5.2 Neoadjuvant Nivolumab and Ipilimumab

5.2.1 Drug Supply

Both nivolumab and ipilimumab will be obtained through commercial drug supply.

5.2.2 Dose Selection

Neoadjuvant nivolumab is delivered at a dose of 3 mg/kg over 30 minutes every 21 days via IV infusion on day 1 and day 22 of each 42-day cycle for 2 doses (1 cycle).

Neoadjuvant ipilimumab is delivered at a dose of 1 mg/kg over 30 minutes every 42 days via IV infusion on day 1 of each 42-day cycle for 1 dose (1 cycle). When given on the same day as nivolumab, ipilimumab is to be given following nivolumab infusion.

5.2.3 Dose Modification

Adverse events (both non-serious and serious) associated with nivolumab or ipilimumab exposure may represent an immunologic etiology. These adverse events may occur shortly after the first dose or several months after the last dose of treatment. No dose reduction for nivolumab or ipilimumab is recommended. In general, withhold nivolumab and ipilimumab for severe (Grade 3) immune-mediated adverse reactions. Permanently discontinue the agents for life-threatening (Grade 4) immune-mediated adverse reactions, recurrent severe (Grade 3) immune-mediated reactions that require systemic immunosuppressive treatment, or an inability to reduce corticosteroid dose to 10 mg or less of prednisone or equivalent per day within 12 weeks of initiating steroids.

Dosage modifications for nivolumab or ipilimumab in combination for adverse reactions that require management different from these general guidelines are summarized in the prescribing information (Appendix).

Dosing interruptions are permitted in the case of medical / surgical events or logistical reasons not related to study therapy (e.g., elective surgery, unrelated medical events, patient vacation, and/or holidays). Subjects should be placed back on study therapy within 3 weeks of the scheduled interruption, unless otherwise discussed with the Principal Investigator. The reason for interruption should be documented in the patient's study record.

5.4 Adjuvant Nivolumab and Ipilimumab

Following surgery, patients will have 6-8 weeks of recovery prior to the initiation of adjuvant immunotherapy. Cross-sectional imaging will be obtained prior to starting adjuvant therapy and will be repeated every 6 weeks while on therapy. Adjuvant immunotherapy with nivolumab and ipilimumab will be administered according to the same dosing and schedule as it was given in the neoadjuvant phase, but with the first cycle to include nivolumab alone.

The first 2 cycles in the adjuvant phase will include nivolumab delivered at a dose of 3 mg/kg over 30 minutes every 21 days via IV infusion on day 1 and day 22 of each 42-day cycle for 4 doses (2 cycles) and ipilimumab delivered at a dose of 1 mg/kg over 30 minutes every 42 days via IV infusion on day 22 of each 42-day cycle for 2 doses (2 cycles). When given on the same day as nivolumab, ipilimumab is to be given following nivolumab infusion. Following these first 2 adjuvant cycles, nivolumab will be delivered alone at the same dose, route, and rate every 21 days on days 1 and 22 of each 42-day cycle, continuing until 1 year post-operatively.

6.0 ADDITIONAL METHODOLOGY

6.1 Trial Blinding/Masking

This is an open-label trial; therefore, the investigator and subject will know the treatment administered.

6.2 Randomization or Treatment Allocation

There will be no randomization. All patients that meet criteria will be enrolled in the single arm.

6.3 Stratification

No stratification will be done.

6.4 Concomitant Medications/Vaccinations (allowed & prohibited)

Medications or vaccinations specifically prohibited in the exclusion criteria are not allowed during the ongoing trial. If there is a clinical indication for one of these or other medications or vaccinations specifically prohibited during the trial, discontinuation from trial therapy or vaccination may be required. The final decision on any supportive therapy or vaccination rests with the investigator and/or the subject's primary physician.

6.4.1 Acceptable Concomitant Medications

All treatments that the treating investigator considers necessary for a subject's welfare may be administered at the discretion of the treating investigator in keeping with the community standards of medical care. All concomitant medication will be recorded on the case report form (CRF) including all prescription, over-the-counter (OTC), herbal supplements, and IV medications and fluids. If changes occur during the trial period, documentation of drug dosage, frequency, route, and date may also be included on the CRF.

All concomitant medications received within 28 days before the first dose of trial treatment and 30 days after the last dose of trial treatment should be recorded. Concomitant medications administered after 30 days after the last dose of trial treatment should be recorded as well.

6.4.2 Prohibited Concomitant Medications

Subjects are prohibited from receiving the following therapies during the Treatment Phase of this trial:

- Immunotherapy not specified in this protocol
- Chemotherapy not specified in this protocol
- Investigational agents not specified in this protocol
- Radiation therapy
- Live vaccines within 30 days prior to the first dose of trial treatment and while participating in the trial. Examples of live vaccines include, but are not limited to, the following: measles, mumps, rubella, varicella/zoster, yellow fever, rabies, BCG, and typhoid vaccine.
- Systemic glucocorticoids while on nivolumab and ipilimumab for any purpose other than to modulate symptoms from an event of clinical interest of suspected immunologic etiology. The use of physiologic doses of corticosteroids may be approved after consultation with the Principal Investigator.

Subjects who, in the assessment by the treating investigator, require the use of any of the aforementioned treatments for clinical management should be removed from the trial. Subjects may receive other medications that the treating investigator deems to be medically necessary.

The Exclusion Criteria describes other medications that are prohibited in this trial.

There are no prohibited therapies during the Post-Treatment Follow-up Phase.

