4.7 Discontinuation of Study and Participant Withdrawal

Discontinuation of study intervention does not represent withdrawal from the study. As data on clinical events beyond study intervention discontinuation may be important to the study, they must be collected through the participant's last scheduled follow up, even if the participant has discontinued study intervention. Therefore, all participants who discontinue study intervention prior to completion of the protocol-specified treatment period will still continue to participate in the study.

Participants may discontinue study intervention at any time for any reason or be discontinued from the study intervention at the discretion of the investigator should any untoward effect occur. Also, a participant may be discontinued from study intervention by the investigator if study intervention is inappropriate, the study plan is violated, or for administrative and/or other safety reasons. A participant must be discontinued from study intervention but continue to be monitored in the study for any of the following reasons:

1. The participant or participant's legally acceptable representative requests to discontinue study intervention.
2. Any occurrence of another malignancy that requires treatment.
3. Unacceptable AEs or toxicities
4. The participant interrupts study intervention administration for >28 consecutive days
5. The participant has a medical condition or personal circumstance which, in the opinion of the investigator, placed the participant at unnecessary risk from continued administration of study intervention.
6. The participant has a confirmed positive serum or highly-sensitive urine pregnancy test.

A participant must be withdrawn from the study if the participant or participant's legally acceptable representative withdraws consent from the study. If a participant withdraws from the study, they will no longer receive study intervention or be followed at scheduled protocol visits.

Lost to Follow-up

If a participant fails to return to the clinic for a required study visit and/or if the site is unable to contact the participant, the following procedures are to be performed:

1. The site must attempt to contact the participant and reschedule the missed visit. If the participant is contacted, the participant should be counseled on the importance of maintaining the protocol-specified visit schedule.

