6.6.3 Use in Pregnancy

If a subject inadvertently becomes pregnant while on study, the subject will immediately be removed from the study. The treating investigator and/or their designee will contact the subject at least monthly and document the subject's status until the pregnancy has been completed or terminated. The outcome of the pregnancy will be reported to the Principal Investigator.

If a male subject impregnates his female partner the study personnel at the site must be informed immediately and the pregnancy reported to the Principal Investigator and followed as described above.

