7.16 Survival Follow-up

Once a subject experiences confirmed disease progression or starts a new anti-cancer therapy, the subject moves into the survival follow-up phase and should be contacted by telephone every 12 weeks to assess for survival status until death, withdrawal of consent, or the end of the study, whichever occurs first.

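### Sections 6.4.2 and 6.6.3 remove patients from the trial where 4.7, 6.4, 7.6.3 and 7.16 keep them in follow-up; applied literally, 6.4.2 could bias the Kaplan-Meier OS curve upward

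*Combined protocol and SAP*

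**What the plan says.** All references are to the combined protocol and SAP.

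- **6.4.2** lists therapies prohibited in the Treatment Phase (off-protocol immunotherapy, chemotherapy and investigational agents, radiation, live vaccines, and systemic glucocorticoids with exceptions). Subjects who "require the use of any of the aforementioned treatments for clinical management should be removed from the trial".
- **6.4**, its parent section, says for prohibited medications or vaccinations only that "discontinuation from trial therapy or vaccination may be required".
- **6.6.3** says that on pregnancy "the subject will immediately be removed from the study", with contact at least monthly until the pregnancy ends.
- **4.7** states that "Discontinuation of study intervention does not represent withdrawal from the study". Its list opens with "A participant must be discontinued from study intervention but continue to be monitored in the study for any of the following reasons", and item 6 reads "The participant has a confirmed positive serum or highly-sensitive urine pregnancy test". The only mandatory withdrawal from the study is for withdrawn consent; for those who withdraw, "they will no longer receive study intervention or be followed at scheduled protocol visits".
- **7.16** says: "Once a subject experiences confirmed disease progression or starts a new anti-cancer therapy, the subject moves into the survival follow-up phase". Contact is by telephone every 12 weeks until death, withdrawal of consent or end of study. **7.6.3** agrees for new anti-cancer therapy.
- **7.15** collects disease status only until new anti-neoplastic therapy, progression, death or end of study.
- **2.2** times OS and PFS from enrollment. **8.2** estimates both by Kaplan-Meier, calls the secondary analyses primarily descriptive, reads a tail on the curve as evidence of long-term survival, and gives no censoring rule.

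**The concern.** Section 4.7 separates stopping treatment from leaving the study, and says that leaving ends scheduled visits. Against that background, removal from the trial or study in 6.4.2 and 6.6.3 has a plain literal meaning that a site could act on. Site staff cannot both remove a pregnant subject from the study and keep her monitored in it. Nor can they both remove a patient who needs chemotherapy from the trial and telephone every 12 weeks until death.

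The statistical stake is OS. Kaplan-Meier assumes that censored patients carry the same later risk as those still followed. Patients who need off-protocol chemotherapy, radiation or immunotherapy during treatment plausibly carry a higher risk. Censoring them at removal would lift the curve. The trial has 37 patients and no control arm, and 8.2 proposes to interpret the tail by eye. Section 8 does not settle the matter: it has no censoring rule, and the prespecified data-handling guidelines that 4.7 mentions for missing data do not appear there.

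**Working it through.** **1. The passages side by side**

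| Situation | One instruction | The other |
|---|---|---|
| Pregnancy | 6.6.3: out of the study at once | 4.7 item 6: stop intervention, stay monitored |
| Needs off-protocol chemotherapy, radiation or immunotherapy | 6.4.2: out of the trial | 6.4: trial therapy may have to stop; 7.6.3 and 7.16: survival follow-up once new anti-cancer therapy starts |

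The pregnancy conflict is direct. The prohibited-therapy conflict is direct for anti-cancer treatments. For live vaccines and non-exempt steroids it is with 4.7 and 6.4 only.

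**2. The plan's own figures**

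There is no stated OS or PFS figure, event count or removal rate to reproduce. The one design figure (N = 37, 80% power for the test of major pathologic response at 0.5 against about 0.7) does not depend on this point.

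**3. Possible size of the OS bias if removal ends follow-up**

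Inputs:
- Median OS without removal: 53 months, the section 3.2.1 figure for CRS+HIPEC. Exponential survival is assumed.
- Share q marked for removal: 10%, 15%, 20% (assumed; about 4 to 7 of 37).
- Removal time R: uniform over months 1 to 12 (assumed). Death before R is possible.
- Median survival after removal: 12 or 24 months (assumed). Section 3.2.1 gives 12 months for untreated disease, not for this group.
- No administrative censoring before month 18.

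Let h0 = ln 2/53 and h1 = ln 2/m, where m is the median after removal.

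Before removal everyone has hazard h0, so a curve that censors at removal estimates
S0(18) = exp(-18·h0) = 2^(-18/53) = 0.790.

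For those marked for removal, true survival averages over R. With c = h1 - h0,
S1(18) = exp(-18·h1) × [exp(12c) - exp(c)]/(11c).

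- m = 12: exp(-18·h1) = 0.3536, c = 0.04468, bracket term = 1.3505, so S1 = 0.477.
- m = 24: exp(-18·h1) = 0.5946, c = 0.01580, bracket term = 1.1096, so S1 = 0.660.
- m = 53 (removal unrelated to prognosis): S1 = S0 = 0.790.

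True OS is (1 - q)·S0 + q·S1, so bias = q·(S0 - S1).

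| q | m = 12: true OS, bias | m = 24: true OS, bias | m = 53: bias |
|---|---|---|---|
| 10% | 0.759, 3.1 points | 0.777, 1.3 points | 0 |
| 15% | 0.743, 4.7 points | 0.771, 2.0 points | 0 |
| 20% | 0.728, 6.3 points | 0.764, 2.6 points | 0 |

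Simulated 37-patient trials give the same biases to within 0.1 point.

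For scale, the binomial standard error of 18-month OS with 37 patients and full follow-up is sqrt(0.743 × 0.257/37) = 0.072, about 7 points.

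**4. A different model**

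Take exponential time to progression and from progression to death, each with median 12, 18 or 24 months, and remove 10% to 50% of those who progress within 14 months. Kaplan-Meier OS at 24 months is then about 1 to 10 points too high. With medians of 18 months the true value is 0.763, and the curve reads 0.776, 0.802 and 0.833 when 10%, 30% and 50% of these progressors are removed. Random removal of 1 patient in 37 leaves it at 0.763.

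**5. PFS**

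A patient treated off protocol because of documented progression has already had the PFS event. For one without documented progression, 7.15 ends disease-status collection at the new therapy whatever 6.4.2 says, and the 7.16 call covers survival status only. The PFS gap is therefore a missing rule for new therapy, and it would remain even if 6.4.2 were reworded.

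**The case against.** The strongest reply is that most of the text points to continued follow-up. Section 4.7 says that stopping treatment is not withdrawal, 6.7 refers to 4.7 for details, 6.4 mentions only trial therapy, and 7.6.3 and 7.16 cover new anti-cancer therapy explicitly. A site that follows those sections loses no OS data. This stands: the bias is conditional. It does not remove the contradiction, because 6.4.2 and 6.6.3 are stated rules and no section says which prevails.

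It is also fair that OS and PFS are secondary and descriptive, that the removal rates are assumed, and that even 6.3 points is within one standard error. Random error, however, has no fixed direction and is shown by a confidence interval; this bias runs upward whenever removed patients fare worse, and no interval reveals it.

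Three stronger readings are tempting and not supported:
- *Everyone removed is doing badly.* Section 6.4.2 also covers live vaccines. It exempts steroids for suspected immunologic events and lets physiologic doses be approved. Pregnancy is not clearly prognostic and would be rare.
- *Safety and feasibility data are lost.* Nothing says that collected data are discarded. Section 7.17.2.1 records adverse events to 30 days after treatment ends, and 7.6.3 and 7.14 place the safety visit before new therapy. Feasibility in 2.2 counts patients who complete neoadjuvant treatment and reach surgery, so a patient removed earlier simply does not count as a success.
- *PFS is biased by 6.4.2 in the same way as OS.* See step 5 of the working.

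**Conclusion.** The contradiction is established from the text: direct for pregnancy (6.6.3 against 4.7 item 6), and clear for off-protocol anti-cancer therapy (6.4.2 against 4.7, 6.4, 7.6.3 and 7.16). A reader might infer that OS and PFS will be informatively censored. The documents support only that OS could be, if removal under 6.4.2 is carried out as an end to follow-up and the removed patients have a worse prognosis.

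Under those two conditions, 18-month OS would read about 1 to 6 points too high for 10-20% removed and a 12- to 24-month median after removal. These inputs are assumptions; under the second model the range at 24 months is about 1 to 10 points. With prognosis-neutral removal the bias is zero. The primary analysis and the sample size are unaffected. The point deserves correction because the conflicting rules are explicit and the remedy costs little.

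**What to change.** - **6.4.2 and 6.6.3:** reconcile with 4.7, 6.4, 7.6.3 and 7.16 so that, whatever is decided about study treatment, removal does not end survival follow-up.
- **8.2, OS:** state that deaths after removal count as events, and that only withdrawal of consent, loss to follow-up or data cut-off censors OS.
- **8.2, PFS:** state how new anti-cancer therapy without documented progression is handled. If progression after that point is to count, 7.15 must also change, since it ends disease-status collection there and the 7.16 call cannot supply it.

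No position is taken on which therapies are prohibited or when treatment should stop.

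The cost is a few sentences in three sections. The 12-weekly survival calls are already scheduled, so OS needs no new procedure. Only a decision to keep assessing progression after new therapy would add work.

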6.5 Supportive Care Guidelines

Subjects should receive appropriate supportive care measures as deemed necessary by the treating investigator. Suggested supportive care measures for the management of adverse events with potential immunologic etiology are outlined below. Where appropriate, these guidelines include the use of oral or intravenous treatment with corticosteroids as well as additional anti-inflammatory agents if symptoms do not improve with administration of corticosteroids. Note that several courses of steroid tapering may be necessary as symptoms may worsen when the steroid dose is decreased. For each disorder, attempts should be made to rule out other causes such as metastatic disease or bacterial or viral infection, which might require additional supportive care. The treatment guidelines are intended to be applied when the treating investigator determines the events to be related to the study treatment.

It may be necessary to perform conditional procedures such as bronchoscopy, endoscopy, or skin photography as part of evaluation of the event.

- **Pneumonitis:**

- For **Grade 2 events**, treat with systemic corticosteroids. When symptoms improve to Grade 1 or less, steroid taper should be started and continued over no less than 4 weeks.
- For **Grade 3-4 events**, immediately treat with intravenous steroids. Administer additional anti-inflammatory measures, as needed.
- Add prophylactic antibiotics for opportunistic infections in the case of prolonged steroid administration.

- **Diarrhea/Colitis:**

Subjects should be carefully monitored for signs and symptoms of enterocolitis (such as diarrhea, abdominal pain, blood or mucus in stool, with or without fever) and of bowel perforation (such as peritoneal signs and ileus).

- All subjects who experience diarrhea/colitis should be advised to drink liberal quantities of clear fluids. If sufficient oral fluid intake is not feasible, fluid and electrolytes should be substituted via IV infusion. For Grade 2 or higher diarrhea, consider GI consultation and endoscopy to confirm or rule out colitis.
- For **Grade 2 diarrhea/colitis** that persists greater than 3 days, administer oral corticosteroids.
- For **Grade 3 or 4 diarrhea/colitis** that persists > 1 week, treat with intravenous steroids followed by high dose oral steroids.
- When symptoms improve to Grade 1 or less, steroid taper should be started and continued over no less than 4 weeks.
- **Type 1 diabetes mellitus (if new onset, including diabetic ketoacidosis [DKA]) or \geq Grade 3 Hyperglycemia, if associated with ketosis (ketonuria) or metabolic acidosis (DKA)**
 - For **T1DM** or **Grade 3-4 Hyperglycemia**
 - Insulin replacement therapy is recommended for Type I diabetes mellitus and for Grade 3-4 hyperglycemia associated with metabolic acidosis or ketonuria.
 - Evaluate patients with serum glucose and a metabolic panel, urine ketones, glycosylated hemoglobin, and C-peptide.
- **Hypophysitis:**

- For **Grade 2** events, treat with corticosteroids. When symptoms improve to Grade 1 or less, steroid taper should be started and continued over no less than 4 weeks. Replacement of appropriate hormones may be required as the steroid dose is tapered.
- For **Grade 3-4** events, treat with an initial dose of IV corticosteroids followed by oral corticosteroids. When symptoms improve to Grade 1 or less, steroid taper should be started and continued over no less than 4 weeks. Replacement of appropriate hormones may be required as the steroid dose is tapered.

- **Hyperthyroidism or Hypothyroidism:**

Thyroid disorders can occur at any time during treatment. Monitor patients for changes in thyroid function (at the start of treatment, periodically during treatment, and as indicated based on clinical evaluation) and for clinical signs and symptoms of thyroid disorders.

- **Grade 2** hyperthyroidism events (and **Grade 2-4** hypothyroidism):
 - In hyperthyroidism, non-selective beta-blockers (e.g. propranolol) are suggested as initial therapy.
 - In hypothyroidism, thyroid hormone replacement therapy, with levothyroxine or liothyroinine, is indicated per standard of care.
- **Grade 3-4** hyperthyroidism
 - Treat with an initial dose of IV corticosteroid followed by oral corticosteroids. When symptoms improve to Grade 1 or less, steroid taper should be started and continued over no less than 4 weeks. Replacement of appropriate hormones may be required as the steroid dose is tapered.

- **Hepatic:**

- For **Grade 2** events, monitor liver function tests more frequently until returned to baseline values (consider weekly).
 - Treat with IV or oral corticosteroids
- For **Grade 3-4** events, treat with intravenous corticosteroids for 24 to 48 hours.
- When symptoms improve to Grade 1 or less, a steroid taper should be started and continued over no less than 4 weeks.

- **Renal Failure or Nephritis:**

- For **Grade 2** events, treat with corticosteroids.
- For **Grade 3-4** events, treat with systemic corticosteroids.

- When symptoms improve to Grade 1 or less, steroid taper should be started and continued over no less than 4 weeks.

Management of Infusion Reactions:

Discontinue nivolumab and ipilimumab in patients with severe (Grade 3) or life-threatening (Grade 4) infusion-related reactions. Interrupt or slow the rate of infusion in patients with mild (Grade 1) or moderate (Grade 2) infusion-related reactions.

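### Section 6.5 starts steroids later for Grade 3 or 4 treatment-related diarrhea/colitis (after more than 1 week) than for Grade 2 (after more than 3 days)

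*Combined protocol and SAP*

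**What the plan says.** Section 6.5 (Supportive Care Guidelines) lists suggested management for adverse events that may be immune-related. Its scope is stated as follows: "The treatment guidelines are intended to be applied when the treating investigator determines the events to be related to the study treatment".

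The diarrhea/colitis block has two steroid rules:

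- Grade 2: oral steroids for an event "that persists greater than 3 days, administer oral corticosteroids".
- Grade 3 or 4: steroids for an event "that persists > 1 week, treat with intravenous steroids followed by high dose oral steroids".

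The same block asks staff to watch for enterocolitis and for signs of bowel perforation. It also advises fluids for all affected subjects, and asks that GI consultation and endoscopy be considered from Grade 2 upwards. None of these steps carries a waiting period.

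**The concern.** Guidance graded by severity should not ask for a longer wait at the more severe grade. Here the route of treatment does escalate, from oral steroids to intravenous followed by high-dose oral, but the timing runs the other way. Section 5.2.3 describes Grade 3 immune-mediated reactions as severe and Grade 4 as life-threatening. Taken literally, section 6.5 has life-threatening colitis wait longer for steroids than a Grade 2 event.

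The stake is patient safety. Nivolumab plus ipilimumab is given both before and after cytoreductive surgery that may include visceral resections (sections 5.3 and 5.4). Staff may turn to this section during an acute event, and a clinician who followed the bullet as written would start steroids later in the sicker patient.

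**Working it through.** The plan has no figure to reproduce here. The check sets the rules side by side and then looks for any other text that would override them.

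**1. The two thresholds in the diarrhea/colitis block.** Onset is counted as day 1.

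- Grade 2: more than 3 days, so steroids from day 3 + 1 = 4.
- Grade 3 or 4: more than 1 week, that is more than 7 days, so steroids from day 7 + 1 = 8.
- Difference: 8 − 4 = 4 days, with the more severe grades later.

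The Grade 2 bullet names Grade 2 alone. The bullet just above it, on GI consultation, covers Grade 2 and higher, so the text uses the wider range where it wants it. The 3-day rule therefore cannot be read as extending to Grade 3 or 4.

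**2. The other steroid rules in section 6.5.**

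| Disorder | Grade 2: wait before steroids | Grade 3-4: wait before steroids | Grade 3-4 rule |
|---|---|---|---|
| Pneumonitis | none stated | none | "immediately treat with intravenous steroids" |
| Diarrhea/colitis | more than 3 days | more than 7 days | see the plan's text above |
| Hypophysitis | none stated | none stated | "treat with an initial dose of IV corticosteroids followed by oral corticosteroids" |
| Hyperthyroidism | no steroid rule | none stated | "Treat with an initial dose of IV corticosteroid followed by oral corticosteroids" |
| Hepatic | none stated | none stated | "treat with intravenous corticosteroids for 24 to 48 hours" |
| Renal failure or nephritis | none stated | none stated | systemic steroids |

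- Grade 3-4 steroid rules: 6, of which 5 state no wait. Diarrhea/colitis is the exception.
- Disorders with a steroid rule at both levels: 5 (all except hyperthyroidism). In 1 of the 5, diarrhea/colitis, the higher grade starts later.

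**3. Could other text supply an earlier trigger?**

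- Section 5.2.3 says when to withhold or stop the drugs and refers to the prescribing information for dosage modifications. It does not set a steroid start.
- Section 6.4.1 lets the investigator give any treatment considered necessary.
- Section 6.4.2 exempts steroids given for suspected immune events from its prohibition and sets no minimum duration.

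The last two permit earlier steroids, but neither tells anyone to give them. The 1-week bullet is thus the only written trigger for Grade 3 or 4.

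**4. Who is affected.** A patient at Grade 2 for more than 3 days should already be on oral steroids before any worsening. The longer wait applies to events that start at Grade 3 or 4, or reach it before Grade 2 steroids have begun. For example, a patient at Grade 2 on day 1 who worsens to Grade 3 on day 2 leaves a rule that would have started steroids on day 4. The new rule starts them on day 8 if the week runs from onset, or on day 2 + 7 = 9 if it runs from the day Grade 3 was reached. The protocol does not say which count applies.

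**The case against.** The strongest reply is that the guidance does not bind. Section 6.5 calls its measures suggestions and leaves supportive care to the investigator's judgement. Sections 6.4.1 and 6.4.2 allow steroids from day 1. Study drug is withheld at Grade 3 and stopped at Grade 4 (section 5.2.3), and fluids and GI work-up are not delayed. All of this stands, and it limits the likely harm. It does not put the order right: the purpose of section 6.5 is to guide the investigator's judgement, and here it guides it the wrong way.

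A second reply is that the five-of-six comparison proves less than it seems to. Diarrhea/colitis is also the only disorder with a persistence condition at Grade 2, and only pneumonitis actually says treatment is immediate; the other four are silent on timing. That is fair. The count does not show that every persistence condition is an error. The case rests on the comparison within the block, Grade 2 against Grade 3 or 4, which the count does not touch. Nor can time to exclude infection explain the order: the section asks for other causes to be ruled out in every disorder, and that gives no reason for a longer wait at the higher grade of the same disorder.

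A third reply is that harm is not quantified. That is correct. The documents give no incidence of colitis and no estimate of what a delay does to the risk of perforation. They also do not show which threshold was intended.

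**Conclusion.** The point holds and should be fixed. As written, the suggested steroid start for treatment-related Grade 3 or 4 diarrhea/colitis is about 4 days later than for Grade 2. The conclusion rests on the plain reading that each bullet applies to the grades it names and that 1 week means 7 days. The number of patients affected cannot be estimated from the documents. No endpoint, sample size or analysis changes.

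**What to change.** Delete the persistence condition from the Grade 3 or 4 diarrhea/colitis bullet, so that it calls for intravenous and then high-dose oral steroids with no waiting period. This brings it into line with the other five Grade 3-4 steroid rules in section 6.5. If the clinical team wants to keep a persistence requirement, it should be no longer than the 3 days used for Grade 2, and the text should say whether the days run from onset or from the day the grade was reached. The clinical team should confirm the final wording.

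The cost is a correction to one bullet. It needs no new visits, procedures or data.
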